### **13.2.2. Subject Populations for Analysis**

The following analysis populations will be defined for this study:

**Intent-to-Treat:** will include any subject randomized into the study that receives a dose of study drug and that has completed at least one post-baseline efficacy measurement while on study medication;

**Safety:** Any subject randomized into the study that receives a dose of study drug;

**Per-Protocol:** Any subject who is randomized and receives the protocol required study drug exposure and required protocol processing.

Efficacy analyses will be performed on the Intent-to-Treat population and the Per-Protocol population. Safety summaries will be based on Safety set. Subject characteristics will be presented for all subjects randomized.

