## **13. STATISTICS**

### **13.1. Sample Size and Accrual**

Based on a two-sided t-test with the 5% significance level, the planned sample size of 75 subjects per arm (a total of 150 subjects) provides around 86% power to detect a mean difference of 0.8 point in the average of nausea severity score assuming the standard deviation of 1.6 in each treatment group.

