#### **13.2.1. General**

Statistical analyses will be performed using two-sided tests.

Data will be summarized by treatment group (and by visit when applicable), with respect to demographic and baseline characteristics, efficacy variables, and safety variables.

Summary statistics will include the mean, N, standard deviation, median, minimum, and maximum values for continuous variables, and frequencies and percentages for categorical variables.

Continuous efficacy variables will be analyzed using a mixed-effect model for repeated measures (MMRM) and/or an analysis of covariance (ANCOVA) model. The models will be described in the SAP.

For the analyses of change from baseline, only subjects with a baseline and at least one (1) post-baseline measure will be included in the analysis. Unless otherwise specified, baseline is defined as the latest non-missing observation across all the visits in the screening phase, before the active study drug begins. Endpoint will be the latest non-missing observation across all the post-baseline visits in the evaluation phase.

Low enrolling sites will be pooled for analysis and the pooling algorithm will be determined prior to breaking the blind. The goal of pooling low enrolling sites is to have a sufficient number of subjects per treatment group within a site for the analysis models and for the evaluation of the

treatment-by-site interaction for the primary endpoint. Unless otherwise specified, the pooled sites will only be used in the analyses where site is included. The actual sites rather than the pooled sites will be specified in data listings.

Categorical variables will be analyzed using the Cochran-Mantel-Haenszel (CMH) test blocking on sites, and Fisher's exact test will be used when site is not adjusted (mainly for safety assessment).

Details of the model and the analyses will be specified in the SAP. All statistical analyses will be performed using SAS®, Version 9.1.3 or higher.

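### The set labelled Intent-to-Treat in Section 13.2.2 is a modified ITT set: entry depends on a dose and on an on-drug efficacy measurement, and no all-randomized efficacy analysis is described

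*Combined protocol and SAP*

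**What the plan says.** Section 13.2.2 defines the Intent-to-Treat population in two steps. It "will include any subject randomized into the study that receives a dose of study drug", and the subject must also be one who "has completed at least one post-baseline efficacy measurement while on study medication". The Per-Protocol set is narrower, because it requires the protocol's drug exposure and procedures.

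On use, the same section states: "Efficacy analyses will be performed on the Intent-to-Treat population and the Per-Protocol population". All randomized subjects appear only in descriptive reporting: "Subject characteristics will be presented for all subjects randomized", and Section 13.2.3 reports disposition for them.

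For analyses of change from baseline, Section 13.2.1 adds that "only subjects with a baseline and at least one (1) post-baseline measure will be included in the analysis". Section 13.3.1 lists the methods for the primary outcome: MMRM, ANCOVA with LOCF for subsequent missing values, and observed cases. Section 13.2 leaves full detail to a statistical analysis plan, whose text is not part of the document available here.

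**The concern.** Randomization protects the comparison of everyone randomized. The set used for efficacy is instead chosen by events that follow randomization. Not taking the first dose is the lesser worry, since in a blinded trial that decision should not depend on the arm. Stopping before an on-drug measurement is different: early intolerance, for example, can differ between drug and placebo.

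The words requiring that the measurement be made on drug go beyond what the model needs. An MMRM of change needs a post-baseline value, and Section 13.2.1 already says so. It does not need that value to have been recorded before the subject stopped. The plan does intend to collect efficacy data from subjects who stop: Section 5.1.2.2 includes efficacy assessments at early termination, and Section 6.3 asks for efforts to obtain the Visit 4 procedures. At stake are a mild tilt in the estimate if exclusions differ by arm, and a result labelled intent-to-treat that rests on a selected set.

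**Working it through.** **1. The plan's own figure.** Section 13.1 says that 75 per arm "provides around 86% power to detect a mean difference of 0.8 point", with SD 1.6 and a two-sided 5% t-test. The standardized difference is 0.8/1.6 = 0.5, and the noncentrality is 0.5 × √(75/2) = 3.06. The t-test gives 86.0% and the normal approximation 86.5%, so the figure reproduces. It assumes 75 analysed per arm. It does not test the population definition, but it supplies the SD and n used below.

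**2. Who can be excluded.**

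| Randomized subject | In the set as defined? | Usable by the listed methods if Intent-to-Treat meant all randomized? |
|---|---|---|
| Never dosed, no post-baseline data | No | No |
| Dosed, no post-baseline data | No | No |
| Dosed, stops before any on-drug measurement, gives efficacy data at early termination | No | Yes, for the scales recorded |
| Dosed, at least one on-drug measurement, then stops | Yes | Yes |

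The third row is where the on-drug clause acts by itself. Section 9.1.4 shows what that visit yields: mGCSI, mPAGI-SYM, PGI-C, PAGI-QOL and CGI-S, which are secondary outcomes. The primary outcome comes from the diary.

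Section 13.2.2 does not name the instrument that counts as an efficacy measurement. Section 10 lists the diary first among the efficacy scales, so one diary entry should qualify. If a visit scale were meant, the first scheduled one is Visit 3 at Day 14 ± 3, and the period in which a subject could be excluded would run to about two weeks.

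**3. Size of a possible bias.** No exclusion rate is given, so all inputs in this step except n and SD are assumptions. Let shares e_T and e_C be excluded, and let excluded subjects do g points worse than retained ones. The mean over all randomized in an arm is the retained mean minus e × g, so the retained-set difference is inflated by

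(e_T − e_C) × g.

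- Equal shares and equal g: 0.
- 3 of 75 active, 0 placebo, g = 1.5: the mean over all randomized is (72 × 1.5 + 3 × 0)/75 = 1.44 against 1.50 in those retained. The overstatement is 0.06 point, and 0.06/0.8 = 7.5% of the target difference.
- 10% against 5%, g = 0.8 to 1.6: 0.04 to 0.08 point.
- 10% against 2%, g = 0.8 to 1.6: 0.06 to 0.13 point.

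**4. Effect on type I error.** With SE = 1.6 × √(1/n_T + 1/n_C), n_T = 75(1 − e_T), n_C = 75(1 − e_C), and a shift b from step 3, the two-sided error is Φ(b/SE − 1.96) + Φ(−b/SE − 1.96).

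- 10% against 5%: SE = 0.272, giving about 5.3% to 6.0%.
- 10% against 2%: SE = 0.270, giving about 5.7% to 7.6%.

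These last two scenarios are pessimistic for a trial with a daily diary.

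**The case against.** The strongest reply is that the on-drug clause is an entry test met by a single measurement. Dosing starts on the evening of Day 0 and the diary is completed daily, so a dosed subject must stop before one on-drug entry to be excluded. Section 6.3 treats discontinuation as leaving the study and describes no further diary collection after that. For the primary outcome, the observed data lost to this clause are therefore close to nil. This stands, and it limits the size. It does not justify the label or the clause.

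It is also fair that disposition is reported by arm for all randomized subjects, that this is a Phase IIa proof-of-concept study, and that the separate statistical analysis plan may say more. The requirement in Section 13.2.1 for a baseline and a post-baseline value is a data requirement for computing change, not a second fault.

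A reader might infer two stronger things. One is that the need for a post-baseline value affects only the MMRM, so that the imputation-based or CMH analyses would recover everyone once the set is redefined. The documents do not support this: LOCF fills only subsequent gaps, observed cases adds nobody, and no non-responder rule is stated for the CMH tests. The other is that off-drug data are removed from subjects already in the set. The definition does not say that.

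**Conclusion.** The point holds as one of definition and labelling, with a real but narrow loss of data. The set called Intent-to-Treat is a modified ITT set, and the protocol text describes no efficacy analysis of all randomized subjects. The on-drug clause can discard observed early-termination data, mainly on secondary scales.

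The size is probably small: about 0.06 point against 0.8 in the one-sided example, zero if exclusion and prognosis are the same in both arms, and up to 0.13 point in the more adverse scenario. All of these rest on assumed exclusion rates and outcomes. The conclusion would change if the separate statistical analysis plan redefines the set. The correction is worth making because it is cheap, not because the trial's result is likely to turn on it.

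**What to change.** In Section 13.2.2, or in the statistical analysis plan before database lock as Section 13.2 allows:

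- Define Intent-to-Treat as all randomized subjects, analysed as randomized.
- Delete the on-drug condition, so that all observed post-baseline efficacy data are used.
- Rename the present set modified ITT, keep it as supportive, and state that a diary entry counts as an efficacy measurement if that is what is meant.
- Report the number excluded from each efficacy set by arm, with reasons.
- Add one sensitivity analysis that imputes randomized subjects with no post-baseline data, for example reference-based multiple imputation. No multiple imputation is planned now, and without it the new definition would not bring these subjects into any estimate.

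The cost is wording, one added sensitivity analysis, and a possibly slightly less favourable estimate.

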### **13.2.3. Subject Disposition**

Study completion and reasons for discontinuation for all randomized subjects in the double-blind phase will be summarized for each treatment group. Discontinuations by reason will be tabulated by visit for each treatment group.

Time to discontinuation due to adverse events, lack of efficacy and for any reason will be analyzed using Kaplan-Meier survival techniques; the log-rank test will be used for group comparison.

### **13.2.4. Demography and Other Baseline Data**

Demographic data and subject characteristics at screening/baseline will be listed and summarized by treatment group for all randomized subjects using descriptive statistics.

Past and current medical history will be summarized by treatment group using the system organ class (SOC) as coded using the Medical Dictionary for Regulatory Activities (MedDRA) coding dictionary.

Past medical conditions will be defined as an onset date prior to randomization (Visit 2) and resolved (not on-going) as of Visit 2. Current medical conditions, defined as an onset date on or after the date of randomization (Visit 2) or an onset date prior to randomization (Visit 2) and unresolved (on-going) as of Visit 2, will be reported separately, but similarly to the past medical conditions. If both a past and a current (on-going) medical condition record are indicated for a condition, the condition will be presented under current medical conditions only.

### **13.2.5. Study Medication**

The number of subjects at each visit will be summarized by treatment group.

The compliance to study medication, as recorded in the CRF, will also be summarized by treatment group. The proportion of subjects who are significantly noncompliant in the double-blind phase will be summarized by treatment groups.

### **13.2.6. Prior/Concomitant Therapy**

Any medications or therapy present before the first dose of study medication (Visit 2) will be considered as prior medications. Concomitant medications (medications present while on study medication) will be recorded throughout the study and at early discontinuation. These medications will be coded using the WHO-drug dictionary. The number of subjects from the Safety Population using prior or concomitant medications will be categorized by the WHO-drug category and preferred term, and presented for each treatment group. In any given category (e.g., drug category) a subject will be counted only once.

## **13.3. Efficacy Data Analysis**

### **13.3.1. Primary Outcome and Methodology**

The primary efficacy outcome measure will be change from baseline to Day 28 in the weekly average of daily nausea severity score. A repeated measures analysis employing a restricted maximum likelihood (REML)-based, mixed-effects model approach (MMRM) will be used to analyze the primary efficacy outcome. The MMRM model will include the fixed, categorical effects of treatment group assignment, visit, treatment group-by-visit interaction and pooled site as well as the fixed, continuous covariates of baseline symptom score and the baseline symptom score-by-visit interaction. A detailed description of the MMRM model will be included in the SAP.

In addition to the MMRM model, an analysis of covariance (ANCOVA) model will also be applied. The last-observation-carried-forward (LOCF) will be used to impute any subsequent missing data. The model will have baseline as a covariate, and the fixed, categorical effects of treatment group assignment, pooled site. An observed cases (OC) analysis will also be performed.

As stated previously, any changes in the statistical methods that occur prior to database lock will be documented in the SAP and will not require a protocol amendment.

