**Primary Endpoint:**

Change from baseline to Day 28 in weekly average of daily individual nausea severity scores (0=none, 1=very mild, 2= mild, 3=moderate, 4=severe, 5=very severe)

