**Table 2: VP-VLY-686-2301 Treatment Arms**

Arm	Total Daily Dose	AM Dose	PM Dose
Tradipitant BID	170 mg	85 mg tradipitant	85 mg tradipitant
Placebo	0 mg	Placebo	Placebo

The study is divided into four phases: the screening phase, the evaluation phase, the open label extension phase, and the continued open label extension phase. The screening phase includes screening and baseline visits where eligibility for the study will be assessed. The evaluation phase includes 4 weeks of placebo-controlled, double-blind, randomized treatment. Daily diaries will be collected throughout both phases of the study. At the end of the 28-day evaluation phase, those subjects who completed this phase enroll into an 8-week open-label extension (OLE) where each subject will receive the same dose of tradipitant utilized in the randomized segment of the study (85 mg bid, approximately 12 hours apart). Subjects who complete the 8 week open label phase can return and enroll into a 52-week continued open label extension phase (COLE).

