**9.1.4. Visit 4 (Study Day 28 ± 3 days)**

- Full PE (excluding pelvic, rectal and breast examinations unless clinically indicated)
- Laboratory evaluations (HbA1C, hematology, chemistry (including eCLcr; based on the Cockcroft-Gault equation), urinalysis, thyroid stimulating hormone (TSH), thyroxine (T4), and urine drug screen)
- Serum pregnancy test and collection of menstrual cycle information (for females of child-bearing potential)
- Pharmacokinetic blood sample
- ECG
- Semi-supine routine vital signs (body temperature, respiratory rate, blood pressure, and pulse) and weight
- Adverse Event query
- Concomitant medication review
- Since last visit C-SSRS
- Review diary
- Collect diary
- Modified Gastroparesis Cardinal Symptom Index (mGCSI)
- Modified PAGI-SYM (mPAGI-SYM)
- Patient Global Impression of Change (PGI-C)
- Patient Assessment of Upper Gastrointestinal Disorder Quality of Life (PAGI-QOL)
- Clinical Global Impression of Severity (CGI-S)
- Study medication collection and review
- Records EOP
- Review of Inclusion criteria (only for subjects that are continuing to the OLE phase)

- Dispense Study Drug (only for subjects that are continuing to the OLE phase)

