#### 20.1.4. Selection and Withdrawal Criteria of Subjects for the OLE Phase

##### 20.1.4.1. Inclusion Criteria

A subject is eligible for enrollment into the OLE phase of this study if he/she meets the following criteria:

- Has completed the randomization phase through Visit 4 (Study Day 28);
- Is willing to provide an additional written informed consent for the OLE phase if enrolled in study prior to OLE becoming available.

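### Could the Day-28 weekly nausea average take in open-label diary days, or be set against a single day's baseline score?

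*Combined protocol and SAP*

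**What the plan says.** The synopsis gives the primary endpoint as "Change from baseline to Day 28 in weekly average of daily individual nausea severity scores", and Section 13.3.1 repeats it in nearly the same terms: "The primary efficacy outcome measure will be change from baseline to Day 28 in the weekly average of daily nausea severity score". Neither place says which diary days make up the week.

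The timing rules around the end of the double-blind period are:

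- Section 9.1.4 is headed "Visit 4 (Study Day 28 ± 3 days"), so the visit may fall on Days 25 to 31. Its task list includes "Collect diary", recording the end of the phase, and "Dispense Study Drug (only for subjects that are continuing to the OLE phase").
- Section 5.1 states: "The evaluation phase includes 4 weeks of placebo-controlled, double-blind, randomized treatment". It adds: "At the end of the 28-day evaluation phase, those subjects who completed this phase enroll into an 8-week open-label extension".
- Section 20.1.4.1 makes a subject eligible for the extension if he or she "Has completed the randomization phase through Visit 4 (Study Day 28").
- Section 20.1.3 moves former placebo subjects to tradipitant. The synopsis (Overall Design) and Section 20.1.11 keep the daily diary running.

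Section 13.2.1 supplies general rules. Unless something else is specified, baseline is the last non-missing observation over the screening visits before active drug. Endpoint is the last non-missing observation over the post-baseline visits of the evaluation phase. Section 13.2 leaves the full methodology to the SAP. No SAP text is readable in the public document, and Section 6.1 and most of Table 3 are blacked out or missing.

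**The concern.** Suppose a programmer codes the Day-28 week as calendar Days 22-28. A placebo subject seen on Day 25, who goes straight into the extension, would then contribute three days of diary scores recorded on tradipitant. Subjects on tradipitant do not change drug, so the contamination sits in one arm only. If the drug works, it pulls the primary contrast toward zero.

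The baseline raises a second question. The diary yields one score per day, so the default rule, read word for word, would set a single day's score against a seven-day average. A one-day score is noisier, and covariate adjustment would recover less precision.

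Both points touch the primary endpoint, and both could be settled in a sentence or two. That is why they looked worth raising.

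**Working it through.** **The plan's own figure.** Section 13.1 gives 75 per arm, a difference of 0.8, SD 1.6 and a two-sided 5% t-test. The noncentrality is 0.8 / (1.6 × √(2/75)) = 3.06 on 148 degrees of freedom. Power is 86.0% (86.5% by the normal approximation), so the stated 86% is right.

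**Open-label days per subject.** Assume a calendar week of Days 22-28. Assume also that the first open-label entry comes the day after Visit 4, because the entry on the visit day looks back 24 hours (Section 10.1.1).

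- Visit on Day 25: 3 of 7 days (43%)
- Visit on Day 26: 2 of 7 (29%)
- Visit on Day 27: 1 of 7 (14%)
- Visit on Days 28-31: none

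**Average share, under two assumed visit patterns.**

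- Visits spread evenly over Days 25-31: (3 + 2 + 1)/7 = 0.857 days, and 0.857/7 = 12.2%.
- Visits clustered at Day 28 (weights 1, 2, 3, 4, 3, 2, 1): (1×3 + 2×2 + 3×1)/16 = 0.625 days, and 0.625/7 = 8.9%.
- With Days 21-27 instead, the shares are 6.1% and 3.6%.

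**Effect on the contrast.** Difference = 0.8 × (1 − share × q). Here q is the proportion entering the extension directly, multiplied by the fraction of the treatment effect reached on those days. Neither factor is in the documents. Power is from the unadjusted t-test.

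| Week, visit pattern | q = 1 | q = 0.5 | q = 0.25 |
|---|---|---|---|
| Days 22-28, even | 0.702, 76.1% | 0.751, 81.5% | 0.776, 83.9% |
| Days 22-28, clustered | 0.729, 79.1% | 0.764, 82.8% | 0.782, 84.5% |
| Days 21-27, even | 0.751, 81.5% | 0.776, 83.9% | 0.788, 85.0% |
| Days 21-27, clustered | 0.771, 83.5% | 0.786, 84.8% | 0.793, 85.4% |
| Week ending at Visit 4 | 0.800, 86.0% | 0.800, 86.0% | 0.800, 86.0% |

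**Which row does the plan describe?**

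- Section 13.2.1 confines Endpoint to the evaluation phase, and Section 5.1 defines that phase as double-blind treatment.
- The primary model in Section 13.3.1 is built on visits, which fits a week aligned to Visit 4 better than fixed calendar days.
- Section 9.1.4 collects the diary and closes the phase at Visit 4.
- Section 20.1.13 gives extension data their own exploratory summaries. Putting those days into the primary endpoint would cross that line.

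The last row is the natural reading.

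**Baseline.** Take 1.6 as the SD before adjustment. Assume a day-to-day intraclass correlation (ICC) of 0.4 to 0.7 and a baseline-to-Week-4 correlation ρ of 0.3 to 0.5. The reliability of an m-day mean is m×ICC / (1 + (m − 1)×ICC), and residual variance is proportional to 1 − ρ² × reliability. For ICC 0.4 the reliability is 0.40 for one day and 2.8/3.4 = 0.82 for seven. With ρ = 0.5 the residual variances are 0.900 and 0.794, a ratio of 1.13.

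| ρ, ICC | Variance ratio, 1 day to 7 | Power, 1 day | Power, 7 days |
|---|---|---|---|
| 0.3, 0.4 | 1.041 | 87.2% | 88.5% |
| 0.3, 0.7 | 1.024 | 88.2% | 88.9% |
| 0.5, 0.4 | 1.133 | 89.4% | 92.7% |
| 0.5, 0.7 | 1.079 | 91.8% | 93.6% |

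The loss is 0.7 to 3.3 points. A score taken before dosing is unaffected by treatment, so the choice adds no bias.

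**The case for a change.** The case for a change is that the passages pointing to double-blind data are rules about visits and phases. None assigns a daily diary entry to a week. The extension criterion treats Visit 4 as Day 28, while the window permits Day 25. If the intent is clear, writing it down costs almost nothing, and doing so before unblinding removes a choice that could otherwise be made with results in view. A seven-day baseline would need no new data, since Section 5.1.1.2 already requires at least 24 screening entries.

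Part of this stands: the readable text does not list the days, and a complete SAP should. It does not show a fault in the plan, for three reasons.

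- The harm needs a calendar week that nobody wrote. The 76.1% also needs evenly spread visits, an immediate full effect and direct entry by everyone. The last conflicts with Visit 4a, which exists because some subjects finished before the extension was available. It also ignores the baseline adjustment in the planned models. With the correlations above and a seven-day baseline, the same diluted difference of 0.702 gives about 79-86%.
- The one-day baseline requires treating a home diary entry as a screening-visit observation. It also requires reading a change in a weekly average as having a weekly average at one end only. Sections 5.1.1 and 5.1.1.1 speak of baseline diary data as something collected over time.
- Section 13.2 places this level of detail in the SAP. Its absence from the text we can read does not show that it is absent from the plan.

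**Conclusion.** The concern does not hold as a reason to change the plan. It identifies a missing detail, the exact diary window, which the protocol leaves to the SAP and which its other provisions lead analysts to fill with double-blind entries only. On that reading the dilution is zero and the stated 86% power stands. The figures of 76-85% apply only under an assumed calendar week, together with assumed visit timing, direct entry and speed of effect. The baseline point rests on a strained reading of a default rule. Even if that reading were adopted, it would cost 0.7 to 3.3 points under the assumed correlations, bring no bias and leave adjusted power at 87-92%.

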**Overall Design:**

This is a multicenter, randomized, double-blind, placebo-controlled study to be conducted in the United States. One hundred fifty (150) subjects diagnosed with gastroparesis, who satisfy the selection criteria for the study, will be randomized to one of two treatment groups. Randomization will be stratified by disease etiology (idiopathic or diabetic), and enrollment for either of the etiologies will be capped at 60% of the total sample size.

The study is divided into four phases: the screening phase, the evaluation phase, the open label extension phase, and the continued open label extension phase. The screening phase includes a screening visit to evaluate subjects' preliminary eligibility for the study. During the screening phase, subjects will collect diary data for at least 4 weeks. The evaluation phase includes 4 weeks of randomized double-blind treatment. Daily diaries will be completed during all phases. Clinical evaluations will occur at Screening, Baseline, Week 2 and Week 4. At the end of the 28-day evaluation phase, those subjects who completed this phase will enroll into an 8-week open-label extension (OLE), where each subject will either continue (if previously on active) or be switched to (if previously on placebo) the same daily dose of tradipitant as the randomized portion of the study (85 mg bid, approximately 12 hours apart). Patients who complete the 8 week open-label extension phase will return for a 52 week continued open label extension phase (COLE).

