## 5. INVESTIGATIONAL PLAN

### 5.1. Overall Study Design and Plan: Description

This is a randomized, double-blind, placebo-controlled study to be conducted in the United States. Approximately one hundred fifty (150) patients diagnosed with gastroparesis of either diabetic or idiopathic origin satisfying the selection criteria for the study will be randomized 1:1 to tradipitant treatment or matching placebo (Table 2). Randomization will be stratified by disease etiology (idiopathic or diabetic), and enrollment for each etiology will be capped at 60% of the total sample size.

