### **13.3.2. Secondary Efficacy Analysis**

The secondary efficacy outcomes include:

- Other Gastroparesis Core Symptoms: vomiting, early satiety, post-prandial fullness, and upper abdominal pain;
- mGCSI
- mPAGI-SYM
- PGI-C
- PAGI-QOL
- GTBS
- CGI-S

Continuous endpoints will be summarized and analyzed in a manner similar to the primary endpoint. Details of the analysis will be described in the SAP.

Categorical variables will be evaluated as described in the SAP. Time to event data will be analyzed using the Kaplan-Meier method, and the treatment group differences will be tested by the log-rank test. Details of the analysis will be described in the SAP.

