### **13.5. Subgroup Analysis**

The subgroup analysis (such as, gender, age, etiology, baseline illness severity etc.) for efficacy variables and safety variables may be conducted as described in the SAP.

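### Randomization is stratified by etiology, but neither the listed MMRM nor the ANCOVA adjusts for it; if etiology predicts change in nausea, the primary test is slightly conservative

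*Combined protocol and SAP*

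**What the plan says.** Section 5.1 states "Randomization will be stratified by disease etiology (idiopathic or diabetic"), and the synopsis (Overall Design) adds that "enrollment for either of the etiologies will be capped at 60% of the total sample size". No other stratification factor is stated.

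Section 13.3.1 lists the categorical terms of the primary model: "The MMRM model will include the fixed, categorical effects of treatment group assignment, visit, treatment group-by-visit interaction and pooled site". The continuous terms are baseline score and baseline-by-visit. For the supporting ANCOVA it says: "The model will have baseline as a covariate, and the fixed, categorical effects of treatment group assignment, pooled site". Etiology is in neither list.

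The continuous secondary endpoints inherit the same structure under Section 13.3.2: "Continuous endpoints will be summarized and analyzed in a manner similar to the primary endpoint". Section 13.2.1 blocks the CMH tests for categorical variables on site only. Within the statistics section, etiology appears only in 13.5, as an optional item: "The subgroup analysis (such as, gender, age, etiology, baseline illness severity etc.) for efficacy variables and safety variables may be conducted".

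Sections 13.2 and 13.3.1 leave the full model description to a SAP whose text is not part of the document reviewed.

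**The concern.** Stratifying on a factor keeps it balanced between arms, so the real sampling variation of the treatment difference no longer contains that factor's contribution. A model without the factor does not know this. It leaves the factor's variance in the residual and reports a standard error that is too large whenever the factor predicts outcome. The test then rejects less than 5% of the time under the null and gives up some power.

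Here the models adjust for pooled site, which is not a stated stratification factor, and not for the one factor that is. At stake is efficiency and a test run at its nominal level. The treatment estimate is not biased and false positives are not inflated.

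**Working it through.** **Inputs from the documents.** 75 per arm, 1:1 allocation, two-sided 5% test, difference 0.8, SD 1.6 (Sections 5.1 and 13.1). Each etiology is capped at 60%, so the split lies between 50:50 and 60:40.

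**Assumptions.** The documents give no etiology effect, so *g*, the difference between etiologies in mean change in nausea, is taken as 0, 0.5 and 1.0 point. Total SD is held at 1.6. A single Day 28 endpoint stands in for the repeated-measures contrast, and dropout is ignored.

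**Stated power.** Section 13.1 says the sample size "provides around 86% power to detect a mean difference of 0.8 point". The noncentrality is 0.8 / (1.6 × √(2/75)) = 0.8 / 0.2613 = 3.06. With 148 df the noncentral t gives 86.0%, so the figure reproduces.

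**Variance due to etiology.** With split *p*, this is p(1 − p)g². At 60:40:

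- g = 0.5: 0.24 × 0.25 = 0.06, which is 2.3% of 2.56. Within-stratum SD = √2.50 = 1.581.
- g = 1.0: 0.24 × 1.00 = 0.24, which is 9.4% of 2.56. Within-stratum SD = √2.32 = 1.523.

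**Type I error without etiology.** The true standard error uses the within-stratum SD, and the model's uses 1.6. Actual level = 2 × P(Z > 1.96 × 1.6 / SD_within).

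- g = 0.5: 1.96 × 1.012 = 1.983, giving 4.7%.
- g = 1.0: 1.96 × 1.050 = 2.059, giving 4.0%.

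**Power at a true difference of 0.8** (plain model, no baseline or site). Without etiology, the critical difference is computed with SD 1.6 and the sampling error with SD_within. With etiology, the noncentral t has 147 df and SD_within.

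| g | Type I error without | Power without | Power with |
|---|---|---|---|
| 0 | 5.0% | about 86% | about 86% |
| 0.5 | 4.7% | 86.4% | 86.8% |
| 1.0 | 4.0% | 87.3% | 89.2% |

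A 50:50 split gives nearly the same result (g = 1.0: 3.9%, then 87.4% and 89.3%).

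**Simulation closer to the planned model.** 20,000 trials per scenario; 90/60 etiology split; permuted blocks of 4 within etiology (assumed); baseline explaining 25% of the non-etiology variance (assumed); 10 pooled sites unrelated to outcome (assumed).

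| g | Type I error, without / with | Power, without / with |
|---|---|---|
| 0 | 5.0% / 5.0% | 92.3% / 92.3% |
| 0.5 | 4.8% / 5.2% | 92.4% / 92.7% |
| 1.0 | 3.9% / 5.1% | 92.7% / 94.4% |

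Monte Carlo error is about 0.15 points for type I error. Without etiology, the mean model standard error against the actual SD of the estimate is 0.235 against 0.232 at g = 0.5 (about 1% too large) and 0.238 against 0.225 at g = 1.0 (about 6% too large).

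**Repeated measures.** With four weekly points, complete data and an etiology effect that grows over the weeks (4,000 runs per setting), an etiology main effect alone brought type I error back to about 5%.

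**The case against.** The strongest reply is that Section 13 is a summary. It defers the full model to the SAP, and a list of terms the model will include does not say that nothing else goes in. That limits the point to the terms the protocol lists. It does not remove it: the list is specific down to the baseline-by-visit interaction, and a deferral adds no term. If the SAP already contains etiology, the action is only to confirm it.

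The second reply is that little is at stake, and this stands. The error is in the conservative direction in a Phase IIa proof-of-concept study. The upper end of the range needs a 1.0-point etiology difference, larger than the 0.8-point drug effect the trial is powered for. At 0.5 point the gain is only 0.3 to 0.5 points of power.

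Third, the calculations favor adjustment somewhat. Baseline and pooled site are already in the models and could carry part of any etiology effect, for example if sites differ in their diabetic mix. Section 7.4.3 gives no block size, and looser balance within strata would reduce the conservatism. Both would shrink the gain; neither would make adjustment harmful.

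**Conclusion.** The point holds as a small efficiency gain, not a validity defect. As listed, the primary and supporting models omit the one factor the trial states it stratifies on. If etiology does not predict change in nausea, nothing is lost. If it does, the test runs below its nominal level (about 4.7% at a 0.5-point difference, about 4.0% at 1.0 point) and forgoes about 0 to 2 points of power, more plausibly half a point or less. The treatment estimate is unbiased and the stated 86% stands. The sizes rest on assumed etiology effects, a single-time-point approximation, good balance within strata and no dropout.

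**What to change.** Add etiology (idiopathic/diabetic) as a fixed effect to the primary MMRM and the ANCOVA, and to the continuous secondary analyses that follow the same model. Pooled site can stay. An etiology-by-visit term may be considered, but the main effect was enough in the repeated-measures check. Record the choice in the SAP before unblinding, so that adjusted and unadjusted results are not chosen between afterwards.

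The cost is one model term and one degree of freedom. No new data are needed, because etiology must be known at randomization. No protocol amendment is needed either: Section 13.3.1 says "any changes in the statistical methods that occur prior to database lock will be documented in the SAP".
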